11.3.3.2. Secondary Analyses

Continuous secondary endpoints will be analyzed using the same methodology as for the primary endpoint, unless otherwise indicated.

For analysis of categorical secondary endpoints, the difference in the predictive marginal proportions will be the basis of comparison between treatment groups.

The corresponding 95% CI and P value will also be presented.

11.3.3.3. Exploratory Analyses

For additional endpoints derived using the baseline prior to Injection 1, descriptive statistics for each variable will be presented for each visit until the end of study and summarized by treatment group and by injection period within each group. For additional endpoints derived using the baseline prior to Injection 2, descriptive statistics for each variable will be presented by treatment group. Efficacy endpoints relative to Injection 2 baseline will only be analyzed for patients who receive Injection 2.

The analysis of all continuous additional endpoints will be performed using an ANCOVA model as described for the single-dose primary endpoint.

Categorical exploratory endpoints will be analyzed using the same methodology as the categorical secondary endpoints.

P values from additional endpoints will be considered nominal and no adjustments for multiplicity will be made.

Subgroup analyses of the primary and secondary endpoints will be performed by age (<65 or \geq 65 years), sex, race (Caucasian or non-Caucasian), and Kellgren-Lawrence grade (2 or 3). Further details will be provided in the SAP.

Mean value, mean change, and percent change from baseline in WOMAC Pain and weekly average daily pain will be plotted over time.

A cumulative distribution plot of percent change in WOMAC Pain by treatment group will be produced for each time point from Injection 1 Baseline through Week 52. Patients who discontinue treatment are defined as non-responders with 0% improvement (no change from Baseline).

11.3.4. Safety and Tolerability Analyses

Safety analyses will be conducted using data from the SAF population (as defined in Section 11.2). Safety variables include physical examination, vital signs assessments (heart rate, respiratory rate, sitting blood pressure, and temperature), clinical laboratory assessments (hematology, chemistry, urinalysis), HbA1c, morning serum cortisol, [REDACTED] 12-lead electrocardiogram (ECG), knee radiographs, concomitant medications/therapies, AEs, and signs and symptoms of adrenal insufficiency. Medical history and AEs will be coded using the Medical Dictionary for Regulatory Activities (MedDRA), and concomitant medication will be coded using the World Health Organization Drug (WHODrug) Global Dictionary.

The safety data will be descriptively summarized by treatment group within each injection period. The safety profile following the first and second injections will be evaluated through the examination of the following comparisons:

1. Group A versus Group B for safety data collected following Injection 2.
2. Safety data in Group A, collected following Injection 1 versus Injection 2.

Continuous safety data will be summarized by visit and include changes from baseline (Injection 1 and/or Injection 2 Baseline). Continuous data will also be converted to categorical values where possible (i.e., below, within, and above normal ranges) and summarized in shift from baseline tables. Categorical safety data collected by visit will be summarized showing the counts and percentages in each category at each visit, as well as shifts from baseline as appropriate.

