8.2. Study Duration

The planned sequence and maximum duration of the study periods for each patient will be as follows:

1. Screening period: up to 4 weeks
2. Injection 1 period: up to 24 weeks following the administration of Injection 1
3. Injection 2 period: up to 28 weeks following the administration of Injection 2

Patients who do not receive Injection 2 will be followed for up to 52 weeks following the administration of Injection 1.

The maximum study duration for each patient is approximately up to 56 weeks.

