8.3.3. Follow-up Assessments

8.3.3.1. Visit 3 (Week 1) and Visit 4 (Week 2)

Patients will return to the study site at Week 1 (± 3 days) and Week 2 (± 3 days) after Injection 1 and have the following procedures performed.

1. Measure vital signs (heart rate, respiratory rate, sitting blood pressure, and temperature) after the patient has been in a sitting position for 5 minutes.
2. Collect serum sample for measurement of cortisol before 9 AM.
3. Review rescue medication use and the diary records. Rescue medication will be dispensed as needed.
4. Complete WOMAC.
5. Complete PGIC.
6. Record concomitant medications use.
7. Record AEs.
8. Ask patients to score their average pain in the index knee for the previous 24 hours by NRS every evening.
9. Ask patients to record their rescue medication use daily in the diary.

8.3.3.2. Visits 5 Through 9 (Every 4 Weeks from Week 4 Through Week 20)

Patients will return to the study site at Week 4 (± 7 days) and every 4 weeks (± 7 days) through Week 20 to have the following procedures performed:

1. Measure vital signs (heart rate, respiratory rate, sitting blood pressure, and temperature) after the patient has been in a sitting position for 5 minutes.
2. Collect blood samples for clinical chemistry, hematology, and HbA1c in a fasted state (Visit 7 only).
3. Collect serum sample for measurement of cortisol before 9 AM.
4. Review training and assessment of knowledge on pain ratings, allowable rescue medication, and entering data into the diary (Visit 7 or as needed).
5. Complete WOMAC.
6. [REDACTED]
7. Complete PGIC.
8. Record concomitant medication use.
9. Record AEs.
10. Review rescue medication use and the diary records. Rescue medication will be dispensed as needed.

11. Ask patients to score their average pain in the index knee for the previous 24 hours by NRS every evening.
12. Ask patients to record their rescue medication use daily in the diary.

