8.3.3.3. Visit 10 (Week 24 and Injection 2)

Patients who have completed through Week 24 and meet the Injection 2 criteria (Section 6.6.3) will receive a second injection of blinded study drug (see Section 7.2) at Week 24 (\pm 7 days). Patients who do not receive Injection 2 may remain in the study unless they choose to withdraw or are withdrawn from the study for other reasons.

The following procedures will be performed (Steps 1 through 17 should be completed before study drug administration):

1. Measure vital signs (heart rate, respiratory rate, sitting blood pressure, and temperature) after the patient has been in a sitting position for 5 minutes.
2. Perform physical examination.
3. Collect serum sample for measurement of cortisol before 9 AM.
4. Collect blood samples for clinical chemistry, hematology, and HbA1c in a fasted state.
5. Perform a posterior-anterior X-ray radiograph for both knees in standing fixed-flexion (approximately 20 degrees), as applicable. This may be performed within 14 days before this visit.
6. Perform 12-lead ECG after the patient has been supine for at least 5 minutes.
7. Collect urine sample for urinalysis.
8. For women of childbearing potential, perform urine pregnancy test (β -hCG) before dosing.
9. Perform drug screen and alcohol breath tests (onsite).
10. Review training and assessment knowledge on pain ratings, allowable rescue medication, and entering data into the diary.
11. Review rescue medication use and the diary records. Rescue medication will be dispensed as needed.
12. Record concomitant medications.
13. Record AEs.
14. Complete WOMAC.
15. [REDACTED]
16. Complete PGIC.
17. Confirm if the patient is disqualified from receiving Injection 2 (see Section 6.6.3).
18. Perform synovial fluid aspiration and administer study drug (Injection 2).

19. Investigator to assess patient for AEs after the injection.
20. Ask patients to score their average pain in the index knee for the previous 24 hours by NRS.
21. Ask patients to record their rescue medication use daily in the diary.

8.3.3.4. Visits 11 and 12 (Weeks 25 and 26) – Injection 2 Follow-up Assessments

Patients who receive Injection 2 will return to the clinic for Injection 2 follow-up assessments 1 week (± 3 days) and 2 weeks (± 3 days) after Injection 2. Patients who do not receive Injection 2 will continue with their follow-up assessments as described in Section 8.3.3.5.

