1. Measure vital signs (heart rate, respiratory rate, sitting blood pressure, and temperature) after the patient has been in a sitting position for 5 minutes.
2. Collect serum sample for measurement of cortisol before 9 AM.
3. Review rescue medication use and the diary records. Rescue medication will be dispensed as needed.
4. Complete WOMAC.
5. Complete PGIC.
6. Record concomitant medications use.
7. Record AEs.
8. Ask patients to score their average pain in the index knee for the previous 24 hours by NRS every evening.
9. Ask patients to record their rescue medication use daily in the diary.

8.3.3.5. Visits 13 Through 18 (Every 4 Weeks from Week 28 Through Week 48)

Patients will return to the study site at Week 28 (± 7 days) and every 4 weeks (± 7 days) through Week 48 to have the following procedures performed:

1. Measure vital signs (heart rate, respiratory rate, sitting blood pressure, and temperature) after the patient has been in a sitting position for 5 minutes.
2. Perform 12-lead ECG after the patient has been supine for at least 5 minutes (Visit 18 only).
3. Collect serum sample for measurement of cortisol before 9 AM.
4. Collect blood samples for clinical chemistry, hematology, and HbA1c (Visits 15 and 18 only) in a fasted state.
5. Perform urinalysis (Visit 18 only).
6. Review rescue medication use and the diary records. Rescue medication will be dispensed as needed.
7. Review training and assessment of knowledge on pain ratings, allowable rescue medication, and entering data into the diary (Visit 15 or as needed).
8. Complete WOMAC.

9. [REDACTED]
10. Complete PGIC.
11. Record concomitant medications use.
12. Record AEs.
13. Ask patients to score their average pain in the index knee for the previous 24 hours by NRS every evening.
14. Ask patients to record their rescue medication use daily in the diary.

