11.3.4.1. Adverse Events

The Medical Dictionary for Regulatory Activities terminology will be used to classify all AEs with respect to system organ class (SOC) and PT.

Treatment-emergent AEs are defined as AEs with onset at the time of or following the start of treatment with study drug through EOS or ET, whichever occurs first.

The number and percentage of patients with AEs will be displayed for each treatment group by SOC and PT. Summaries of AEs by severity and relationship to study drug will also be provided. Serious AEs and AEs resulting in discontinuation of study drug will be summarized separately in a similar manner. Patient listings of AEs, SAEs and AEs causing discontinuation of study drug will be produced.

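### The Group A first- versus second-injection AE comparison sets patient percentages over 24 weeks against percentages over 28 weeks, with no common window or patient-time rate stated

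*Combined protocol and SAP*

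**What the plan says.** Section 5.2 makes the safety of single and repeat doses a secondary objective. Section 11.3.4 sets the unit of summary: "The safety data will be descriptively summarized by treatment group within each injection period". It then names two comparisons: Group A against Group B after Injection 2, and "Safety data in Group A, collected following Injection 1 versus Injection 2".

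Section 11.3.4.1 gives the AE measure: "The number and percentage of patients with AEs will be displayed for each treatment group by SOC and PT". It defines treatment-emergence from first dose to the end of study or early termination, with no separate window for each injection.

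Section 8.2 gives the period lengths: "Injection 1 period: up to 24 weeks following the administration of Injection 1" and "Injection 2 period: up to 28 weeks following the administration of Injection 2".

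Sections 8.3.3.2 to 8.3.4 fix the testing. Chemistry, hematology and HbA1c are drawn at Weeks 12 and 24, and then at Weeks 36, 48 and 52; for the visits from Week 28 to Week 48 the text is "Collect blood samples for clinical chemistry, hematology, and HbA1c (Visits 15 and 18 only) in a fasted state". ECGs are at Week 24, and then at Weeks 48 and 52. The Week 24 tests belong to the first period, because "Steps 1 through 17 should be completed before study drug administration" (Section 8.3.3.3).

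**The concern.** The share of patients with at least one AE rises with time at risk. Comparing a 24-week share with a 28-week share in the same group makes the second injection look somewhat worse even if risk is unchanged.

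The extra draw works in the same direction. Section 8.4.2.1.3 requires laboratory changes that the investigator judges clinically significant to be reported as AEs, so a third draw is a further chance to record one. The documents do not allow that part to be sized.

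This is the plan's only named within-group contrast of a first with a second TLC599 dose. Its two columns will be read side by side, and neither a crude difference nor a crude absence of difference can be taken as the effect of repeating the dose.

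**Working it through.** **The plan's own figures.** 4 + 24 + 28 = 56 weeks and 1 + 1 + 2 + 6 + 2 + 7 = 19 visits. Both match the protocol summary.

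**Scheduled contacts after each injection** (Sections 8.3.3.1 to 8.3.4)

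| | After Injection 1 | After Injection 2 |
|---|---|---|
| Nominal length | 24 weeks | 28 weeks |
| Visits | 8 (Weeks 1, 2, 4, 8, 12, 16, 20, 24) | 9 (Weeks 25, 26, 28, 32, 36, 40, 44, 48, 52) |
| Chemistry/hematology/HbA1c | 2 | 3 |
| ECG | 1 | 2 |
| Urinalysis, physical examination, radiograph | 1 each | 1 each |

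**Effect of window length alone.** Assume no change in risk, full follow-up in both periods, and a hazard in weeks 0-4 after injection that is k times the later hazard. The ratio of cumulative hazards at 28 and 24 weeks is (4k + 24)/(4k + 20):

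- k = 1: 28/24 = 1.1667
- k = 5: 44/40 = 1.10
- k = 10: 64/60 = 1.0667

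The 28-week percentage is 1 − (1 − p)^ratio, where p is the 24-week percentage. The values k = 5 and k = 10 are assumptions; the documents give no AE time course.

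| 24-week p | k = 1 | k = 5 | k = 10 |
|---|---|---|---|
| 10% | 11.6% (+1.6) | 10.9% (+0.9) | 10.6% (+0.6) |
| 20% | 22.9% (+2.9) | 21.8% (+1.8) | 21.2% (+1.2) |
| 40% | 44.9% (+4.9) | 43.0% (+3.0) | 42.0% (+2.0) |

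Group A has about 500 × 2/4 = 250 patients, so +2.9 points at 20% is about 7 extra patients.

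**Do patient-time rates repair it?** Take first events divided by time to first event or end of window, at p = 20%. The 28-week rate over the 24-week rate is 1.00 (k = 1), 0.944 (k = 5) and 0.916 (k = 10). When AEs cluster early, the rate shows a false fall of about 6-8%, so a rate alone only partly repairs the comparison.

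**Where could a common window end?** Section 1.1 times visits from Day 1 with ±7 days.

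- Injection 2 falls 161-175 days after Injection 1, so first-injection follow-up is 23-25 weeks.
- The Week 48 visit is at 336 ± 7 days. From Injection 2 that is 329 − 175 = 154 to 343 − 161 = 182 days, or 22-26 weeks.
- The Week 52 visit is at 364 ± 7 days. From Injection 2 that is 357 − 175 = 182 to 371 − 161 = 210 days, or 26-30 weeks.

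A cut at the Week 48 visit is therefore not a common window. A late Injection 2 lengthens the first side and shortens the second, to 25 against 22 weeks at the extreme. A cut at a fixed number of days removes this. Every patient who stays in the study and keeps to the visit windows has at least 161 days on both sides, and at least 182 days after Injection 2.

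**The case against.** The strongest reply is that Section 11.3 is only a summary and sends details to a SAP. AE windows and exposure adjustment are ordinary SAP content, so the most that can be said is that the supplied text states neither. That stands. A reader might infer that the sponsor has no adjustment planned; the documents do not show that.

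A second reply is that the plan already has a fair comparison. Group A against Group B after Injection 2 is between randomized arms over the same weeks with the same tests. This also stands, and it rules out the inference that the plan has no equal-window view of repeat dosing. Group C is likewise already tabulated by injection period, so a placebo reference for the time trend exists.

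A third is that the effect is small beside sampling error. At 20% with 250 patients, the 95% half-width of a difference is 1.96 × √(2 × 0.2 × 0.8/250) ≈ 7 points if the two percentages are treated as independent, and about 5 points at an assumed within-patient correlation of 0.5. The shift there is 1.2-2.9 points. This is a good reason not to overstate the point, but the shift is systematic and can be removed without new data.

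Two further readings should be resisted:

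- The unequal draws and ECGs might suggest that the laboratory and ECG tables are distorted. Sections 11.3.4.2 and 11.3.4.4 summarize them by time point, so they are not.
- The calculation might suggest that the second injection will on balance look worse. Section 11.2 limits Injection 2 reporting to patients who received it. Section 6.6.3 bars those with adrenal insufficiency through Week 24, and Section 6.7 provides for withdrawal for AEs. That selection may offset or reverse the window effect, so the net direction is unknown.

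**Conclusion.** The point holds in a limited form. As written, the Group A comparison of Injection 1 with Injection 2 uses crude AE percentages over unequal periods, and the supplied text gives no correction. Over the cases shown, window length alone adds 0.6 to 4.9 percentage points to the second-injection figure. This assumes unchanged risk, complete follow-up and a hazard that is either constant or up to 10 times higher in the first 4 weeks; withdrawals would alter it. The contribution of the extra draw and the effect of selection cannot be sized from the documents.

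The comparison is descriptive, with no test or decision rule attached. The correction is worth making because it is cheap and bears on a stated secondary objective, not because it threatens the trial's main conclusions.

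**What to change.** In Section 11.3.4 or the SAP, for the Group A Injection 1 versus Injection 2 AE table and the matching Group C columns:

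- Count AEs with onset within the same fixed number of days after each injection, and show patient-time. One choice is 168 days, ending first-injection follow-up at Injection 2 if that comes earlier. Another is 161 days, which the visit windows allow on both sides. Do not use the Week 48 visit as the cut.
- Keep the full 28-week table. Add exposure-adjusted rates as a supplement, with a note that they can fall falsely when AEs cluster early.
- State beside the table that the Injection 2 set holds only patients who qualified for and received Injection 2. A common window does not remove that selection.

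The cost is a few extra tables and some wording, with no new visits or data. Later AEs, and those found at the Week 52 examination or radiograph, will appear only in the full-period table. A fixed-day cut may also exclude some Week 24 or Week 48 tests. With 161 days, tests done on their nominal day fall outside on both sides, because Week 24 is 168 days after Injection 1 and Week 48 is 336 − 168 = 168 days after Injection 2.

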6. STUDY DESIGN

6.1. Overall Study Design and Plan

This is a Phase 3 randomized, double-blind, placebo- and active comparator-controlled pivotal study. Approximately 500 adult patients with moderate to severe pain due to OA of the knee who meet all entry criteria will be enrolled and randomized into a 2:1:1 ratio to receive TLC599 12 mg (Group A), DSP 4 mg (Group B), or Placebo (normal saline) (Group C) via IA injection into the designated index knee at Baseline (Injection 1). At Week 24, patients will receive Injection 2 per their randomly assigned dosing regimen (Group A, B, or C) via IA injection into the index knee (see Section 6.6.3 for Criteria for Injection 2). Patients who received TLC599 12 mg (Group A) or DSP (Group B) for Injection 1 will receive blinded TLC599 12 mg for Injection 2 and those who received Placebo for Injection 1 (Group C) will receive Placebo for Injection 2.

All patients will be followed for a total of 52 weeks, regardless of whether or not they receive Injection 2. Patients who do not receive Injection 2 will be encouraged to continue in the study through 52 weeks of follow-up. Efficacy and safety of 2 doses of TLC599 will be evaluated in comparison with Placebo and DSP through Week 52.

To enter the study, patients must be at least 40 years of age and have documented diagnosis of OA in the index knee based on American College of Rheumatology (ACR) Criteria for Classification of Idiopathic OA of the knee (the ACR diagnostic criteria is provided in Appendix A). Patients will not be eligible if they have unstable index knee joint as determined by the investigator based on physical examination (with or without buckling or giving way) because of an acute injury (defined as injury within 6 months, e.g., anterior cruciate ligament injury or tear).

The study duration is expected to be up to 56 weeks for each patient, including a Screening period of up to 4 weeks before randomization, Injection 1 Period of 24 weeks and Injection 2 Period of 28 weeks.

Patients will return to the study site at Week 1, Week 2, and every 4 weeks through Week 52 post-dose to complete efficacy and safety assessments as applicable. Patients who receive Injection 2 will return to the clinic for 2 additional follow-up visits (Week 25 and Week 26).

Efficacy will be assessed by WOMAC, numeric rating scale (NRS), [REDACTED] and Patient Global Impression of Change (PGIC) at the time points indicated in the schedule of events (Section 1.1).

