6.6.3. Criteria for Injection 2 (Week 24)

Patients will not continue with Injection 2 if any of the following criteria are met:

2. Occurrence of adrenal insufficiency through Week 24.
3. If female and of childbearing potential, have a positive urine pregnancy test result at Week 24.
4. Positive urine drug or alcohol test result at Week 24. (Drug use allowed with prescription.)

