6.7. Patient Withdrawal from the Study

All patients will be advised that they are free to withdraw from participation in this study at any time, for any reason, and without prejudice. The investigator should make every reasonable attempt to keep patients in the study; however, patients must be withdrawn from the study if they withdraw consent to participate. Patients who do not receive Injection 2 do not need to be withdrawn and will be encouraged to continue in the study through 52 weeks of follow-up. If a patient does not receive Injection 2, it will not be considered a protocol deviation. Investigators must attempt to contact patients who fail to attend scheduled visits by telephone or other means to assess the possibility of an AE being the cause of withdrawal. Should this be the cause, the AE must be documented, reported, and followed as described in Section 9.2.

A participant should be withdrawn from the study if any of the following occurs:

- Pregnancy
- Significant study non-compliance
- Lost to follow-up
- A surgical procedure or IA drug administration in the index knee
- Lack of therapeutic effect that is intolerable or otherwise unacceptable to the patient
- If any clinical AE, laboratory abnormality, or other medical condition or situation occurs such that continued participation in the study would not be in the best interest of the participant
- The investigator or the Sponsor stops the study for any reason

If important restricted medication deviations occur, they should be discussed with the medical monitor before withdrawing the patient from the study.

The investigator should contact the medical monitor to discuss any non-compliance or safety concerns before withdrawing a patient from the study.

The reason for participant withdrawal from the study will be recorded on the eCRF. Patients who sign the ICF, are randomized, and receive study drug, and subsequently withdraw, or are withdrawn from the study, will not be replaced.

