11.2. Analysis Populations

The following analysis populations are planned for this study:

Safety Population (SAF): The Safety Population includes all patients who receive any dose of study drug; the population will be determined for each study period. Injection 1 Period reporting will require that Injection 1 has been received; Injection 2 Period reporting will require that Injection 2 has been received. The SAF population will be the primary population for safety evaluation.

Full Analysis Set (FAS): The FAS includes all randomized patients who receive Injection 1. The FAS population will be the primary population for efficacy analysis, as well as for descriptive summaries other than safety (demographic and baseline, disposition, protocol deviation, medical history, etc.).

Per Protocol Population (PP): The PP Population includes all patients who receive 2 doses of study drug, have primary efficacy evaluation at Weeks 12, 24, and 36, and do not have important protocol deviations affecting primary efficacy evaluation.

Modified Per Protocol (mPP): The mPP Population includes all patients who receive the first dose of study drug, have primary efficacy evaluation at Weeks 12 and 24, and do not have important protocol deviations affecting primary efficacy evaluation.

The **PP** and **mPP** populations will be used for supportive analysis of selected efficacy endpoints. For the PP population, patients must have a valid WOMAC Pain assessment at Baseline, Week 12, Week 24, and Week 36; for the mPP population, patients must have a valid WOMAC Pain assessment at Baseline, Week 12, and Week 24. (A valid assessment is within the analysis visit window and not excluded due to an intercurrent event as described in Section 11.3.3.1).

Important protocol deviations are determined in accordance with the protocol deviation guidance plan. Membership in the PP and mPP analysis populations will be determined after blinded data review of important protocol deviations affecting primary efficacy evaluation before database lock and study unblinding.

If a patient is randomized incorrectly or is administered the incorrect study drug, analyses of the FAS population will be based on the assigned treatment, whereas analyses of all other populations will be based on the actual treatment received.

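### The Group A Injection 1 versus Injection 2 safety comparison sets all treated patients against a subset selected partly on safety, and the plan does not show the Injection 1 events of those who drop out of it

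*Combined protocol and SAP*

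**What the plan says.** Safety of single and repeat doses is a secondary objective (5.2). Group A receives the same product twice. Section 6.1 states: "Patients who received TLC599 12 mg (Group A) or DSP (Group B) for Injection 1 will receive blinded TLC599 12 mg for Injection 2".

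Section 11.3.4 sets the reporting style: "The safety data will be descriptively summarized by treatment group within each injection period". It then lists two comparisons, Group A against Group B after Injection 2, and "Safety data in Group A, collected following Injection 1 versus Injection 2". Adverse events are shown as numbers and percentages of patients (11.3.4.1), with no adjustment for exposure.

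Section 11.2 fixes who is counted in each period: "Injection 1 Period reporting will require that Injection 1 has been received; Injection 2 Period reporting will require that Injection 2 has been received".

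Two provisions remove patients between the periods on safety grounds:
- 6.6.3 lists, among the reasons not to give Injection 2: "Occurrence of adrenal insufficiency through Week 24".
- 6.7 lists a ground for withdrawal that begins "If any clinical AE, laboratory abnormality, or other medical condition or situation occurs such that continued participation in the study" and applies where continuing would not serve the participant's best interest.

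Section 11.3.1.1 tabulates the reasons for not receiving Injection 2. No section links those patients to their events after Injection 1.

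**The concern.** A reader of the two summaries will naturally take a lower percentage after Injection 2 as reassurance about repeat dosing. But a patient whose event after Injection 1 keeps them from Injection 2 counts in the Injection 1 percentage and cannot enter the Injection 2 denominator. If such patients are also more prone to a further event, the Injection 2 percentage falls with no change in the drug's risk, and a modest real increase can be masked. This contrast is one of only two named to evaluate safety after the two injections.

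**Working it through.** The plan states no event rates, no expected share missing Injection 2 and no figure for this comparison, so there is nothing to reproduce. What follows is an illustration.

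**Inputs from the protocol.** 500 patients at 2:1:1 (11.4) give 500 × 2/4 = 250 in Group A. The periods last 24 and 28 weeks (6.1).

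**Assumptions.** The same true risk p follows each injection. Within-patient correlation ρ is 0.2 to 0.5. Of patients without the event after Injection 1, r = 10% miss Injection 2. Of patients with it, a share q miss Injection 2.

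**Formulas.**
- Event in both periods: B = p² + ρp(1 − p). Event in the second only: S = p − B.
- Share receiving Injection 2: D = p(1 − q) + (1 − p)(1 − r).
- Displayed Injection 2 risk: [B(1 − q) + S(1 − r)] / D.
- Injection 1 risk in twice-injected patients: p(1 − q) / D.

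**1. Ordinary adverse event, p = 10%, equal windows.** For ρ = 0.2, B = 0.01 + 0.018 = 0.028 and S = 0.072. For ρ = 0.5, B = 0.055 and S = 0.045. At q = 0.3, D = 0.07 + 0.81 = 0.88. For ρ = 0.2 the displayed risk is (0.0196 + 0.0648)/0.88 = 0.0959.

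| q | Injection 1, all | Injection 2 (ρ 0.2; 0.5) | Ratio (ρ 0.2; 0.5) |
|---|---|---|---|
| 0.10 | 10.0% | 10.0%; 10.0% | 1.00; 1.00 |
| 0.15 | 10.0% | 9.9%; 9.7% | 0.99; 0.97 |
| 0.30 | 10.0% | 9.6%; 9.0% | 0.96; 0.90 |
| 0.60 | 10.0% | 8.9%; 7.4% | 0.89; 0.74 |

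When the event does not predict missing Injection 2 (q = r), there is no bias.

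**2. Event that always bars Injection 2, p = 5%, q = 1.** D = 0.95 × 0.90 = 0.855, and the displayed risk is S × 0.90/0.855. For ρ = 0.2, S = 0.038 gives 4.0%. For ρ = 0.5, S = 0.02375 gives 2.5%. The Injection 1 side still shows 5.0%.

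**3. Period length.** Under a constant hazard, risk over 28 weeks is 1 − (1 − risk)^(28/24). A risk of 5% becomes 5.8%, and 10% becomes 11.6%. Applied as an approximation to the displayed values in step 1:
- q = 0.3: 11.1% and 10.4%
- q = 0.6: 10.4% and 8.5%

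Against 10.0%, Injection 2 looks worse in three of these four cases and better in one.

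**4. Restricting both sides to twice-injected patients, p = 10%, equal windows.** The Injection 1 rate drops to 0.07/0.88 = 8.0% at q = 0.3 and 0.04/0.85 = 4.7% at q = 0.6. Injection 2 to Injection 1 ratios, with no true change, for ρ = 0.2 and 0.5:
- q = 0.3: 1.21 and 1.13
- q = 0.6: 1.90 and 1.56

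All four lie further from 1.00 than the matching ratios in step 1. A simulated McNemar test at nominal 5% (250 patients, 40,000 runs) rejects in 8% to 10% of trials at q = 0.3 and 31% to 48% at q = 0.6.

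**5. What a split would show, p = 10%, q = 0.3.** Of 250 patients, 25 have the event and 7.5 of them miss Injection 2. Of the other 225, 22.5 miss it. Injection 1 risk is 25/250 = 10.0% in total, 17.5/220 = 8.0% in those who went on, and 7.5/30 = 25% in those who did not. The selection becomes visible.

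**The case against.** The case for leaving the plan alone has real substance. The comparison is descriptive, with no test, so no error rate or power is at stake. The protocol calls its statistics section a summary and defers detail to a SAP whose separate text is not in the documents, so any table layout is inferred. Adrenal insufficiency is the only safety bar visible in 6.6.3 (the list as supplied starts at item 2), and most adverse events need not prevent a second injection. Reasons for missing Injection 2 are tabulated, adverse events are listed by patient, and placebo Group C shows how percentages move between periods without active drug.

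All of this limits the size of the point. None of it shows the reader whether the patients missing from the Injection 2 summary were those with events after Injection 1. Group C helps with elapsed time and period length, but safety-related loss need not be the same in both groups.

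Three stronger readings are tempting and not supported:
- That the second injection will look safer than it is. The longer second period pushes the other way, and the rates needed to weigh the two effects are not given.
- That the two summaries describe different patients. The Injection 2 set is contained in the Injection 1 set.
- That a paired test in twice-injected patients is the remedy, because ignoring the pairing costs power. No unpaired test is planned, and step 4 shows that this restriction introduces a larger bias in the opposite direction.

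**Conclusion.** The point holds as a limited one. That selection into the Injection 2 summary depends partly on safety follows from 11.2, 6.6.3 and 6.7 without any assumed rate. Taken alone, it pulls the Injection 2 percentage down for events that predict missing Injection 2 and tend to recur in the same patients. Its size rests on assumptions: with 10% of event-free patients missing Injection 2 and correlation 0.2 to 0.5, it is slight to modest for ordinary adverse events and can reach a halving for an event that always bars Injection 2. The documents do not settle which way the whole display will lean. This is an improvement to a descriptive safety table; the efficacy analyses and sample size are unaffected.

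**What to change.** In 11.3.4, comparison 2, or in the SAP:
- Show the Group A Injection 1 safety summary in total and split by whether the patient received Injection 2, beside the Injection 2 summary.
- State that events which themselves bar Injection 2, such as adrenal insufficiency, are not interpreted from this contrast.
- If wanted, add a within-patient 2x2 count for twice-injected patients (neither period, first only, second only, both) as description only. Do not make a paired difference, confidence interval or test the main result.

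The cost is one extra descriptive table from data already collected, plus a sentence or two of wording. The group that did not receive Injection 2 will be small (about 30 of 250 in step 5), so its percentages will be imprecise and should be shown with counts.
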